#### A2.4 Projects and Statistics:

A Repository Committee will be set up to oversee the work relating to these samples, and to consider requests from other centres for DNA. This committee will consist of the Chief and Lead Investigators, the AR UK selected Trial Steering Committee chairman ([name], University of Glasgow), amongst others, including patient representation. The potential for study of these samples is huge and 3 exemplar projects have been appended. These are merely examples of many possible projects which will be developed by the Repository Steering Committee, in collaboration with others. All requests from academic or pharmaceutical organisations to use the samples would be submitted to an ethics committee for regulatory approval.

The mainstay of analyses based on this resource will be using conventional genetic/serum/plasma statistical methodology, encompassing a range of different analytical approaches and study objectives (including for example, single-locus and haplotype-based studies; biological and positional candidate analyses; replication studies for associations uncovered in other (smaller) populations; logistic regression analyses seeking to dissect LD structure and define aetiological variants; and gene-gene interactions). In addition, the associated longitudinal clinical data will permit analyses of the relationship between genotypes of interest and pertinent outcomes including complication rates; treatment response; survival/mortality; and disease progression. These data will be analysed using multivariate regression and Cox regression methods, including algorithms for repeated measures when appropriate. The trial statistician is [name], (University of Birmingham, The Wellcome Trust Clinical Research Facility), who has ensured the appropriate powering of TRACE RA, and who is involved in the day to day statistical issues of the Trial.

The mainstay of analyses based on this resource will be using conventional genetic/serum/plasma statistical methodology, encompassing a range of different analytical approaches and study objectives (including for example, single-locus and haplotype-based studies; biological and positional candidate analyses; replication studies for associations uncovered in other (smaller) populations; logistic regression analyses seeking to dissect LD structure and define aetiological variants; and gene-gene interactions). In addition, the associated longitudinal clinical data will permit analyses of the relationship between genotypes of interest and pertinent outcomes including complication rates; treatment response; survival/mortality; and disease progression. These data will be analysed using multivariate regression and Cox regression methods, including algorithms for repeated measures when appropriate.

#### A2.5 Facilities and Experience available for the study:

Dundee's Ninewells Hospital is uniquely placed to act as the physical Repository; due to its experience in such studies to date. [name] and [name] have extensive experience in sample preparation for these types of studies.

These include grants from TENOVUS to pilot endothelial studies in a large population of patients with diabetes, the Raynaud's and Scleroderma Association to link the development of carotid vascular disease to certain genotypes in Systemic sclerosis, from the Wellcome Trust UK Case/control study of type 2 diabetes, where all subjects (n=15000) are from Tayside. Tayside is also the principal centre for the recruitment and sample handling for Generation Scotland, with 10,000 individuals to be targeted within the next 2 years, growing to 50,000 Scotland wide by the end of 2011. The robotics and software developed for these large studies will easily accommodate the currently proposed sample throughput.

POPADAD, a Scotland wide 8 year CV mortality trial (n= 1,320) also has Ninewells (and the Dundee applicants) as its core laboratory for sample collection. In addition we have recently developed a "High Volume" genotyping workflow to complement our "high throughput" affymetrix and Illumina systems, where we can cheaply and efficiently genotype 10,000 patient samples for 1 SNP in 2 hours. This system uses both KASPAR indirect allelic discrimination and TAQMAN based allelic discrimination. KASPAR is simpler and much cheaper, but assays that fail on KASPAR will be performed on TAQMAN. Both genotyping techniques are homogenous fluorescent assays that can be performed easily in an automated fashion. Sample reformatting will be performed to 384 well formats on a Xiril liquid handling robot. Reaction

mixtures will be dispensed to 384 using a DEERAC high speed nanodispenser (1-2ul total reaction volumes). PCR will be performed in a H2OBIT ultra-high-throughput thermal cycler (10,000 samples per 2 hour run) and the final genotypes scored using an Applied Biosystem SDS9700. The genotyping project will be analysed, managed and quality controlled using a dedicated genotyping database system (KLUSTERCALLER, KBiosciences).

Standard analytical techniques, in addition to genetic studies, include HPLC-MS, GC-MSMS, ELISA, Spectrophotometry, Affymetrix micro-array, MALDI, proteomics ([name]), flow cytometry, (Luminex Bead array) and Western Blotting.

#### A2.6 Ethical considerations

#### a. Confidentiality, security, ethics and database management

With the implementation of the new data protection act issues of data security and confidentiality are very much in the public eye, as they should be. The mechanisms employed to ensure appropriate security and confidentiality within Ninewells result from years of deliberation and debate and are continually reviewed and updated in parallel with legal and ethical requirements. The exemplar project for Ninewells is the DARTS project, (Diabetes Audit and Research Tayside). As an example of how TRACE RA samples will be treated using DARTS logistics will be explained below.

Clinical information on DARTS is stored on a Structured Query Language (SQL) database. Clinical information is accessed via a Web server and Web browser. The first level of security on clinical data is that imposed by the NHS-NET network. Although DARTS has a presence on the wider Internet, users from the Internet cannot access the DARTS Web Server located within the confines of NHS-NET. A login screen is presented and communications are all encrypted, and access determined by username and password. All attempts to log-on to DARTS and every action subsequently taken are logged producing audit trails. For DARTS anonymous Genetic research we use all the security and confidentiality mechanisms provided by the Microsoft SQL Server V7 platform.

The Tenovus grant award has allowed us to implement a secure system for anonymous genetic case/control studies. Every patient, GP, general practice and hospital clinic represented on the system is allocated a unique randomly generated identifier intended for the purposes of anonymous research. Researchers are then restricted to 'views' of data that use these anonymous identifiers and omit any identifying fields.

Thus, all demographic information is removed except sex, age (in months), and social class (Carstair's Index). For genetic research, only the nurse performing the fieldwork has access to the patients identifying numbers. This nurse does not have access to any other patient-specific data. In addition, although the system administrator (through necessity) has access to all data on the server, the identity of individual genetic markers is not available to him.

The present information sheet is included in Appendix 3. It has been modified according to MRC guidelines to state that products derived from the sample may be used by other researchers and the commercial sector. It includes specific clauses that allow use of samples for RA and wider medical issues including drug response.

All record linkage studies and issues relating to confidentiality, anonymisation of data and dataset security will come under the aegis of the Health Informatics Centre at the University of Dundee. This has an external scientific Advisory Board (chair [name], Professor of Epidemiology, University of Aberdeen) that scrutinises all anonymised record linkage research in Tayside according to published standard operating procedures.

#### b. Administration of the Collection

To maximise the utility of the proposed DNA resource, the collection will be overseen, and access to the resource managed, by the TRACE RA Repository Committee. This steering group would become the custodian of the DNA resource to ensure that maximum benefit is derived from the collection whilst avoiding any unnecessary duplication of genotyping/assaying.

DNA aliquots will be made and master stocks stored in Dundee. Complete plated collections of the DNA (~15ug) will be distributed to the appropriate collaborating centres (see exemplars below ie Manchester). Requests for DNA from external collaborators will be considered. Written applications will be to test specific variants within a gene and standardized data will be required in these requests: data to establish the importance of the gene, the role of the specific variants to be typed eg coding variants, haplotype tagging SNPs etc, details of the assay used for SNPs, preliminary data to give allele frequencies and power calculation.

Permission will be given to exclusively (for one year after permission is granted) test the requested specific SNPS. DNA aliquots may be obtained from Dundee DNA will be given blinded and will include approximately 10% of samples with the most DNA as duplicates to provide a measure of genotyping accuracy. A condition of using the resource will be that all genotyping will be given to the core database so that these data are held centrally; the specific data field however will remain under the custodianship of the scientist performing the study until the data are published. The analysis of the ongoing longitudinal data will be obtained by users of the resource working with the epidemiological team in Dundee. A collaborative framework has been established in the recent SRIF-funded Health Informatics Centre at Ninewells Hospital.

The Health Informatics Centre thus has standard operating procedures that facilitate this collaborative inter-institutional research on anonymised datasets for approved projects. In order to ensure the continuation and the development of this resource, a cost recovery charge will be levied for the supply of DNA and subsequent data analysis to external centres from Dundee/Manchester. Pricing will be determined by the Repository committee based on cost recovery and will be aligned with other UK resources. We would use these funds to support the maintenance and development of the resource at Ninewells beyond the period of this award.

Note: the plasma and serum will be utilised by the TRACE RA Steering Committee as this is a more finite resource.

#### A2.7 Conclusion

We anticipate great demand both nationally and internationally because, to our knowledge there is no comparable publicly available resource.

It will be especially unique because of the longitudinal follow-up of phenotypic data. This Repository will form the basis of an RA Framingham and provide insight into disease mechanisms, complications and drug responsiveness for many years to come.

# APPENDIX 3: SAMPLE PATIENT INFORMATION SHEET, CONSENT FORMS AND GP LETTERS

These are provided as separate documents and will be stored in the master trial file, regional trial unit site files and the centres' site files.

Please see list of documents as follows (All documents will be approved by MREC):

- 1. Patient Information Leaflet Main TRACE RA trial
- 2. Patient Information Leaflet TRACE RA BioBank (Genetic sub-study)
- 3. Patient Information Leaflet & Consent TRACE RA DAS and DAS Biobank (Disease Activity sub-study)
- 4. Consent form Main TRACE RA trial and TRACE RA Biobank (Genetic Substudy)
- 5. Patient Information Leaflet and Consent DNA Collection Only
- 6. GP letter for centres that routinely assess RA patients for 10 year cardiovascular disease risk
- GP letter for centres that do not routinely assess RA patients for 10 year cardiovascular disease risk
   GP referral letter
- 9. Promotional Leaflet TRACE RA information to patients
- 10. Promotional Leaflet TRACE RA information to investigators

## **APPENDIX 4: QUESTIONNAIRES**

These are provided as separate documents and will be stored in the master trial file, regional trial unit site files and the centres' site files.

Please see list of documents as follows (All documents will be approved by MREC):

- 1. Lifestyle questionnaire
- 2. Health Assessment Questionnaire (HAQ)
- 3. EQ5D EuroQol 5 dimensional lifestyle questionnaire
- 4. Patient Global Assessment (Visual Analogue Score)
- 5. Nurse Global Assessment (Visual Analogue Score) (TRACE RA DAS Substudy only)

## APPENDIX 5: DEFINITIONS OF CARDIOVASCULAR ENDPOINTS

An independent cardiovascular endpoint classification committee will review cardiovascular events and all deaths and will classify them according to the WHO MONICA method, or alternative of their choice.

#### Primary Endpoints

Cardiovascular death (excluding definite haemorrhagic stroke (ICD 10: I62-67; and non-coronary cardiac death (I00- etc), non-fatal myocardial infarction, non-fatal stroke or any coronary or non-coronary revascularisation. This will comprise the following, as defined in the subsequent paragraphs:

Coronary heart disease death Fatal presumed ischaemic stroke Other atherosclerotic vascular death Myocardial infarction Myocardial infarction Nonfatal stroke Transient ischaemic attack -a mild cerebrovascular stroke with reversible symptoms that last from a few minutes to several hours Coronary revascularization Non-coronary revascularization (see below for definitions)

#### Secondary endpoints

Cause-specific mortality (coronary, other vascular and non-vascular death separately)

#### **A5.1 FATAL ENDPOINTS**

#### A5.1.1 Coronary heart disease death

Death certificate or equivalent documentation with consistent or underlying or immediate cause plus one of the following:

- i. Preterminal hospitalisation with acute myocardial infarction (see definitions below).
- ii. Previous documented angina or myocardial infarction when no other cause other than atherosclerotic coronary heart disease death could be ascribed as the cause of death.
- iii. Sudden, unexpected cardiac death, involving cardiac arrest, often with symptoms of myocardial ischaemia, and accompanied by presumed new ST segment elevation, or new LBBB, and/or evidence of fresh coronary artery thrombosis by coronary arteriography, but death occurring before blood samples could be obtained, or at a time before the appearance of cardiac biomarkers in the blood.
- iv. Autopsy evidence of acute coronary arterial thrombosis and/or acute myocardial infarction.

#### A5.1.2 Suspect coronary heart disease death

Death certificate or equivalent documentation with consistent underlying or immediate cause but neither adequate preterminal documentation of the event nor previous diagnosis of atherosclerotic coronary heart disease.

#### A5.1.3 Fatal Presumed ischaemic Stroke

Death certificate or equivalent documentation with consistent or underlying or immediate cause plus either:

- i. Preterminal diagnosis of stroke (see definitions below).
- ii. Autopsy evidence of cerebral infarction

# A5.1.5 Other atherosclerotic cardiovascular death (e.g. ruptured aortic aneurysm, mesenteric infarction, peripheral arterial disease):

Death certificate or equivalent documentation with consistent underlying or immediate cause and adequate preterminal documentation of the event.

*Note:* Preterminal documentation and/or information may include hospitalisation for, or diagnosis of, a vascular-related illness for a previous event other than the terminal event.

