### 11. ASSESSMENT OF EFFICACY AND SAFETY

### 11.1 Assessment of efficacy outcomes

The records of English and Welsh randomised patients' will be electronically tagged for mortality with the Office for National Statistics (ONS) and Scottish patients at the Scottish Office's Information and Statistics Division (ISD) as well as the local hospital Trusts' Medical Information departments. Underlying cause of death will be ascertained from death certificates provided by ONS and ISD (which also supply details of times and causes of all hospital admissions in Scotland) supplemented by information from hospital records, including post-mortem examinations, if performed.

Hospital admissions will be ascertained at each centre by matching the patient details with national NHS Hospital Episode Statistics. In addition, non-fatal events will be ascertained regularly by contact with each patient. If necessary additional information will be sought from household members, GP or hospital departments.

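### A5.1.5 requires preterminal documentation and, unlike the coronary and stroke death rules, lists no autopsy alternative, so an autopsy-proven vascular death with no earlier vascular record fails the written rule

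*Protocol*

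**What the plan says.** The primary endpoint list in Appendix 5 includes "Other atherosclerotic vascular death" and refers to the definitions that follow it. A5.1.5 is that definition, and its heading gives ruptured aortic aneurysm as the first example. The rule is "Death certificate or equivalent documentation with consistent underlying or immediate cause and adequate preterminal documentation of the event". A note beneath it adds: "Preterminal documentation and/or information may include hospitalisation for, or diagnosis of, a vascular-related illness for a previous event other than the terminal event".

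Two sister rules are built differently. A5.1.1 asks for a consistent certificate plus one of four items, the last being "Autopsy evidence of acute coronary arterial thrombosis and/or acute myocardial infarction". A5.1.3 asks for a consistent certificate plus either a preterminal diagnosis of stroke or "Autopsy evidence of cerebral infarction".

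Two other places bear on the point. The opening of Appendix 5 says that the independent committee reviews cardiovascular events and all deaths and "will classify them according to the WHO MONICA method, or alternative of their choice". Section 11.1 takes the underlying cause of death from certificates, "supplemented by information from hospital records, including post-mortem examinations, if performed".

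**The concern.** In A5.1.5 the certificate and the preterminal documentation are joined by *and*, so both are mandatory. Autopsy findings come after death and cannot meet the second condition. In A5.1.1 and A5.1.3 autopsy is an alternative to preterminal evidence. Equally well-proven sudden deaths are therefore treated differently according to the vascular bed involved, within one component of the primary endpoint. The committee must then either leave out a proven vascular death or count it against the written definition. At stake is whether this component is classified by a fixed rule or case by case.

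**Working it through.** The plan gives no figure on this point, so the check is mainly a comparison of the rules. Take five deaths, each with a consistent certificate:

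| Death | Evidence | Rule | Counts as written? |
|---|---|---|---|
| 1. Aortic rupture diagnosed in hospital before death | Preterminal record of the event | A5.1.5 | Yes |
| 2. Sudden rupture at home, earlier vascular diagnosis | Autopsy and earlier record | A5.1.5 with its note | Yes |
| 3. Sudden rupture at home, no earlier vascular record | Autopsy only | A5.1.5 | No |
| 4. Sudden death at home, coronary thrombosis | Autopsy only | A5.1.1 item iv | Yes |
| 5. Sudden death at home, cerebral infarction | Autopsy only | A5.1.3 item ii | Yes |

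Deaths 3, 4 and 5 rest on the same kind of evidence, and only death 3 fails. Deaths 2 and 3 have the same autopsy proof and differ only in an earlier record.

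No other category takes in death 3:
- A5.1.2 (suspect death) is for coronary deaths only.
- A5.3.2 (fatal peripheral events) is a secondary endpoint and needs a hospital-verified acute event.
- Treating the autopsy report as documentation equivalent to a certificate meets only the first condition of A5.1.5.

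**How many deaths.** The documents give no mortality rate, no share of deaths in this class and no autopsy rate. The inputs below are assumptions, except the 27000 patient-years and the 434 events of Section 10.1.
- Deaths, at 1 to 2% a year: 27000 × 0.01 = 270, to 27000 × 0.02 = 540.
- In this class, at 1 to 2% of deaths: 270 × 0.01 = 2.7, to 540 × 0.02 = 10.8.
- With no preterminal documentation, at one third to one half: 2.7 / 3 = 0.9, to 10.8 / 2 = 5.4, so about 1 to 5. The upper end is 5.4 / 434 = 1.2% of the target.
- Autopsied, at an illustrative 50%: 0.9 × 0.5 = 0.45, to 5.4 × 0.5 = 2.7.

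The defect concerns only autopsied deaths, so 1 to 5 is a ceiling on these assumptions. Section 10.4 analyses time to first event, so a patient with an earlier non-fatal primary event is already counted, which lowers the number further.

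**Effect on power.** With equal arms, a hazard ratio of 0.76 and two-sided 5%, Schoenfeld's formula gives d = 4(1.960 + 0.842)² / (ln 0.76)² = 417. This reproduces the Appendix 8 figure for patients with events at a 24% reduction; 434 is that table's figure for number of events. Power is Φ(√d × |ln 0.76| / 2 − 1.960):

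| Events lost | From 434 | From 417 |
|---|---|---|
| 0 | 81.6% | 80.0% |
| 4 | 81.2% | 79.6% |
| 13 (3% of 434) | 80.4% | 78.8% |

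Even a loss well above the ceiling costs little more than one percentage point.

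**The case against.** The strongest reply is that the rule is silent on autopsy and does not forbid it. A reader might infer that A5.1.5 refuses autopsy evidence, but no passage says so. Appendix 5 lets the committee choose its classification method and makes it responsible for classifying all possible endpoints, and Section 11.1 puts post-mortem findings into the cause of death. The note to A5.1.5 is also worded as an illustration, so the committee may accept other preterminal information.

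This holds as far as it goes: death 3 is not certain to be lost. It does not repair the rule. Autopsy is named in the two parallel definitions and absent here, and the condition that is stated is one autopsy cannot meet. To count death 3, the committee must depart from the written definition.

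Two further inferences are tempting and are not supported. The first is that every autopsy-proven sudden rupture is lost. The note rescues any patient with an earlier vascular-related diagnosis or hospitalisation. The second is that death 3 is the usual case in this trial. Section 5 excludes known cardiovascular disease deemed to require a statin, including current peripheral arterial disease, which makes the case plausible. But that exclusion applies at entry, does not cover every vascular illness, and diagnoses can accrue during follow-up.

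Nor can Section 3.1 be cited as promising to count atherosclerotic deaths. It speaks of cardiovascular death with coded exclusions; the atherosclerotic aim is in Section 2.2.2 and Appendix 5.

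**Conclusion.** The point holds in a narrow form. As written, A5.1.5 fails an autopsy-proven non-coronary, non-stroke vascular death in a patient with no earlier vascular record, or leaves it to discretion, while equivalent coronary and stroke deaths count. The inconsistency follows from the text and needs no assumption.

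The size does rest on assumptions: at most about 1 to 5 of 434 events, and fewer after allowing for the share autopsied and for earlier first events. A reader might infer a material loss of power or a biased comparison. The arithmetic does not support the first. For the second, the trial is double blind with independent endpoint classification, and nothing in the documents suggests that such deaths would be missed more often in one arm. This is a minor correction to an endpoint definition.

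**What to change.** Before unblinding, reword A5.1.5 in the form of A5.1.3: a certificate or equivalent with a consistent cause, plus **either** adequate preterminal documentation **or** autopsy evidence of the atherosclerotic event. Keep the existing note as an explanation of the first alternative. Deaths already classified in this class should be checked against the new wording, blind to allocation.

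The cost is one clause in Appendix 5 and a review of what is likely to be a handful of deaths. No new data are needed, because Section 11.1 already provides for post-mortem findings where an examination was done.
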